## 7.5            Prior and Concomitant Medications

For the full analysis set and safety analysis set, frequency distributions for usage of concomitant medication on the initial IMP administration day will be calculated.

Table 7.5-1      Usage of Concomitant Medication on the Initial IMP Administration Day	
Variable	Level
Category of diuretic *Concomitant use of diuretic drugs other than loop diuretic, thiazide diuretic, and anti-aldosterone drug is not summarized.	Monotherapy with loop diuretic, Loop diuretic + thiazide diuretic, Loop diuretic + anti-aldosterone drug, Loop diuretic + thiazide diuretic + anti-aldosterone drug
Thiazide diuretic	No, Yes
Anti-aldosterone drug	No, Yes
Drugs for heart failure other than diuretics	No, Yes
CYP3A4 inducers	No, Yes
CYP3A4 inhibitors	No, Yes

## 7.6      Protocol Deviations

For subjects administered IMP, frequency distributions for presence or absence of serious deviations in each CRF classification (Dosing, Inclusion/Exclusion Criteria, Met Withdrawal Criteria But Was Not Withdrawn, Prohibited Concomitant Medications) will be calculated. Frequency distributions of subjects with at least one serious deviation will also be calculated.

# 8      Efficacy Analysis

The following analyses will be performed in the full analysis set and the dose maintenance analysis set.

Efficacy will be comprehensively assessed based on the results of primary and other endpoints.

## 8.1      Primary Efficacy Endpoint

The definition of the primary endpoint is presented in [Section 6.1](#).

### 8.1.1      Primary Efficacy Analysis

The number and percentage of subjects as well as the exact 95% CI based on binomial distribution will be calculated. The same calculations will be performed for body weight on the day after the final administration at the evaluation dose and the day after the final administration. The number and percentage of subjects will also be calculated for each

time point after the start of administration at the evaluation dose (the data to be summarized are from the first day of administration at the evaluation dose to the day after the final administration at the evaluation dose and follow-up period; the same shall apply hereinafter).

Analysis will also be performed using data collected on the first day of administration at the evaluation dose as the baseline.

## **8.2 Secondary Efficacy Endpoints**

### **8.2.1 Percent Change in Body Weight**

For body weight measured on the day after the third day of administration at the evaluation dose, the day after the final administration at the evaluation dose, and the day after the final administration, and their percent changes from baseline, the descriptive statistics (the number of subjects, mean, standard deviation, minimum, median, and maximum) will be calculated, and the 95% CI (based on t-distribution) of the percent changes from baseline in body weight will be calculated. The descriptive statistics will also be calculated for each time point after the start of administration at the evaluation dose.

Analysis will also be performed using data collected on the first day of administration at the evaluation dose as the baseline. In addition, data will be summarized by the number of days that had elapsed since the start of administration (the data to be summarized are from the initial IMP administration day to the day after the final administration; the same shall apply hereinafter).

The figure of percent changes in body weight from baseline will be prepared in individual subjects according to the number of days elapsed (with a reference line of -1.7%).

### **8.2.2 Edematous Symptoms (Edema [Lower Limbs, Eyelids, or Other Sites], Dyspnea, Jugular Venous Distension, Pulmonary Congestion, Cardiothoracic Ratio, Respiration Rate at Rest, Pulse Rate, and Pleural Effusion), Central Venous Pressure (Only Subjects With Central Venous Catheterization), and Retention of Pericardial Effusion (Only Subjects Requiring Echocardiography)**

#### **8.2.2.1 Edema (Lower Limbs, or Other Sites) and Pulmonary Congestion**

A shift table will be prepared for changes in the degree of edema (lower limbs) from baseline to the third day of administration at the evaluation dose, the day of the final administration at the evaluation dose, and the day of the final administration. Another shift table will also be prepared for each time point after the start of administration at the

evaluation dose. Analysis will also be performed using data collected immediately before the start of administration at the evaluation dose as the baseline. In addition, data will be summarized by the number of days elapsed since the start of administration.

In addition, the number and percentage of subjects as well as the exact 95% CI based on binomial distribution will be calculated for the improvement rate (the percentage of subjects who had symptoms at baseline and showed remarkable improvement or improvement after the IMP administration; the same shall apply hereinafter) and the disappearance rate (the percentage of subjects who had symptoms at baseline and whose symptoms resolved after the IMP administration; the same shall apply hereinafter) on the third day of administration at the evaluation dose, the day of the final administration at the evaluation dose, and the day of the final administration. Analysis will also be performed using data collected immediately before the start of administration at the evaluation dose as the baseline (the phrase “after the IMP administration” for the improvement and disappearance rates is read as that of “after the start of administration at the evaluation dose”; the same shall apply hereinafter).

A shift table will be prepared for changes in the degree of pulmonary congestion from baseline through the day after the final administration.

The number and percentage of subjects as well as the exact 95% CI based on the binomial distribution will be calculated for the improvement and disappearance rates on the day after the final administration.

Table 8.2-1		Degree of Improvement of Lower Limb Edema, Other Edema, and Pulmonary Congestion
	Degree of improvement	Criterion
1	Remarkable improvement	Symptom resolution or improvement to at least 2 grades better
2	Improvement	Symptom improvement to 1 grade better (symptom resolution should be assessed as remarkable improvement)
3	No change	No change in the degree of symptom, or no symptom observed throughout the trial period
4	Worsening	Symptom worsening to at least 1 grade worse

### **8.2.2.2 Edema (Eyelids), Jugular Venous Distension, Dyspnea, and Pleural Effusion**

A shift table will be prepared for changes in the degree of edema (eyelids), jugular venous distension, and dyspnea from baseline to the third day of administration at the evaluation dose, the day of the final administration at the evaluation dose, and the day of the final administration. Another shift table will also be prepared for each time point after the start of administration at the evaluation dose. Analysis will also be performed using

data collected immediately before the start of administration at the evaluation dose as the baseline. In addition, data will be summarized by the number of days elapsed since the start of administration.

The number and percentage of subjects as well as the exact 95% CI based on the binomial distribution will be calculated for the disappearance rate on the third day of administration at the evaluation dose, the day of the final administration at the evaluation dose, and the day of the final administration. Analysis will also be performed using data collected immediately before the start of administration at the evaluation dose as the baseline.

A shift table will be prepared for changes in the degree of pleural effusion from baseline through the day after the final administration.

The number and percentage of subjects as well as the exact 95% CI based on the binomial distribution will be calculated for the disappearance rate on the day after the final administration.

### **8.2.2.3      Cardiothoracic Ratio, Respiration Rate at Rest, and Pulse Rate**

For respiration rate at rest and pulse rate measured on the third day of administration at the evaluation dose, the day of the final administration at the evaluation dose, and the day of the final administration, and their changes from baseline, the descriptive statistics will be calculated and the 95% CI (based on the t-distribution) of changes from baseline will be calculated. The descriptive statistics will also be calculated for each time point after the start of administration at the evaluation dose. Analysis will also be performed using data collected immediately before the start of administration at the evaluation dose as the baseline. In addition, data will be summarized by the number of days elapsed since the start of administration.

For the cardiothoracic ratio measured on the day after the final administration and the changes from baseline, the descriptive statistics will be calculated and the 95% CI (based on the t-distribution) of changes from baseline will be calculated.

### **8.2.2.4      Central Venous Pressure**

A list will be prepared.

### **8.2.2.5      Retention of Pericardial Effusion**

A list will be prepared.

## **8.2.3      Daily Urine Volume**

The data based on which the accurate daily volume is measured will be used.

Descriptive statistics of measured values and changes from baseline will be calculated for each time point after start of administration at evaluation dose. An analysis will also be performed using data collected immediately before start of administration at evaluation dose as a baseline. In addition, data will be summarized by the number of days elapsed since start of administration.

The percent changes from baseline will also be summarized in the same manner.

### **8.3 Subgroup Analyses and Analysis by Evaluation Dose**

As a subgroup analysis, the items will also be analyzed for each age group (young age, 6 months to less than 2 years; middle age, 2 years to less than 7 years; and old age, 7 years to less than 15 years).

The same analysis will be performed for each evaluation dose (0.05, 0.15, 0.3, and 0.5 mg/kg/day, a classification entered in a CRF; the same shall apply hereinafter) (in the entire and each age group).

Subgroup analyses and analyses by the evaluation dose of the primary endpoint, percent changes in body weight, and edematous symptoms will be performed for (the day after) the third day of administration at the evaluation dose, the day of (or the day after) the final administration at the evaluation dose, and the day of (or the day after) the final administration (except for the summarization by the number of days that had elapsed since the start of administration).

## **9 Safety Analyses**

The following analyses will be performed in the safety analysis set.

### **9.1 Extent of Exposure**

Frequency distributions of the number of subjects for each number of days of administration from the first day of the treatment period to the completion or discontinuation of the IMP administration (1 to 3 days, 4 to 5 days, 6 to 7 days, 8 to 9 days, and 10 to 13 days) will be calculated. Descriptive statistics will be calculated for the number of days of administration. To be calculated for the entire and by the evaluation dose.

Frequency distributions will be calculated for the evaluation dose.

## **9.2 Adverse Events**

All adverse events (AEs) will be coded by system organ class (SOC) and Medical Dictionary for Regulatory Activities (MedDRA) preferred term (PT). The incidence of the following events will be calculated for all events by SOC and by PT.

- Treatment-emergent AEs (TEAEs)
- TEAEs by severity
- TEAEs with an outcome of death
- Serious TEAEs
- TEAEs leading to discontinuation of the IMP

If there are multiple occurrences of the same event in the same subject, the event with the highest severity will be selected. The above summaries will also be prepared for TEAEs potentially causally related to the IMP.

The above AEs will also be summarized by evaluation dose. In addition, summaries of AEs by the evaluation dose after the start of administration at the evaluation dose will be prepared. Summarization for each age group (young age, 6 months to less than 2 years; middle age, 2 years to less than 7 years; and old age, 7 years to less than 15 years) will also be prepared.

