3.2.4 Extended Treatment With Tolvaptan

Patterns of treatment with tolvaptan including extended treatment are shown in Figure 3.2.4-1. If the investigator or subinvestigator judges that the safety of subjects can continue to be ensured (including ensuring safety by dose reduction) after 3-day administration at the dose decided according to the specification for increasing the dose of tolvaptan (see [Section 3.2.2](#)), administration at that dose may be continued for up to 4 days (for up to 7 days in total).

In the case of an extended treatment with tolvaptan at reduced dose, the total number of administration days should be up to 7 days, which consists of “the days of administration at the dose just before the dose requiring reduction”, “the days of administration at the dose requiring reduction” and “the days of administration at the dose reduced to the next lower dose” (see examples of dose reduction in Figure 3.2.4-1).

[figure not shown]

Figure 3.2.4-1 Patterns of Treatment With Tolvaptan Including Extended Treatment

In principle, tolvaptan will be administered while increasing its dose every 2 days, and then, administered at the dose decided for each individual subject for 3 days. If the dose needs to be reduced before completion of 3-day administration, the dose may be reduced only once. The reduced dose should be regarded as the dose decided for each individual subject, and tolvaptan should be administered at the dose for 3 days. The duration of extended treatment at the reduced dose will be limited.

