3.7.1.5.1 First Day of Administration at Reduced Dose

The investigator or subinvestigator will perform the following procedures.

1) Before tolvaptan administration

The investigator or subinvestigator will perform the following examinations, and then, offer breakfast to the subject.

- Body weight
- Laboratory tests
- Serum or blood sodium concentration
- Serum or blood potassium concentration
- Serum osmolality
- Plasma AVP concentration (on the day after the third day of administration at 0.15, 0.3, or 0.5 mg/kg/day; only subjects from whom samples are available)
- Plasma drug concentration (on the day after the third day of administration at 0.15, 0.3, or 0.5 mg/kg/day): Assessment after breakfast is allowed if it is conducted prior to tolvaptan administration.

The investigator or subinvestigator will instruct the subject to completely discharge the urine immediately after breakfast, and start urine collection and fluid intake measurement to assess the following items.

- Daily urine volume
- Daily fluid intake
- Daily fluid balance
- Urine sodium excretion
- Urine potassium excretion
- Urine osmolality

2) Tolvaptan administration

The investigator or subinvestigator will instruct the subject to take tolvaptan with water after breakfast according to [Section 3.2](#).

3) At a feasible time

- Vital signs
- 12-lead ECG (on the day after the third day of administration at 0.15, 0.3, or 0.5 mg/kg/day)
- Edematous symptoms (after tolvaptan administration)
- Chest x-ray (on the day after the third day of administration at 0.15, 0.3, or 0.5 mg/kg/day)
- Concomitant drugs and therapies

- IMP compliance
- Adverse events

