### **3.2.2 Increasing the Dose of Tolvaptan**

Tolvaptan should be administered according to the following procedure. Daily urine volume should be assessed as "insufficient increase in urine volume" when it is less than 150% of that for the pretreatment observation period (1 day before start of tolvaptan administration), and "sufficient increase in urine volume" when it is at least 150%.

- 1) Tolvaptan administration will be started at 0.05 mg/kg/day, and administration at 0.05 mg/kg/day will be continued for 2 days.
- 2) For subjects with sufficient increase in urine volume on Day 1 or Day 2 of treatment, administration at 0.05 mg/kg/day will be continued for 3 days. For subjects with an insufficient increase in urine volume on Day 1 and Day 2 of treatment, the dose will be increased to 0.15 mg/kg/day on Day 3.
- 3) If a sufficient increase in urine volume is observed following 2-day administration at 0.15 mg/kg/day on Day 3 or Day 4 of the treatment period, administration at 0.15 mg/kg/day will be continued for 3 days. For subjects with an insufficient increase in urine volume on Day 3 and Day 4 of the treatment period, the dose will be increased to 0.3 mg/kg/day on Day 5.
- 4) If a sufficient increase in urine volume is observed following 2-day administration at 0.3 mg/kg/day on Day 5 or Day 6 of the treatment period, administration at 0.3 mg/kg/day will be continued for 3 days. For subjects with an insufficient increase in urine volume on Day 5 and Day 6 of the treatment period, the dose

will be increased to 0.5 mg/kg/day on Day 7, and administration at 0.5 mg/kg/day will be continued for 3 days.

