### **3.2.4 Extended Treatment With Tolvaptan**

If the investigator or subinvestigator judges that the safety of subjects can continue to be ensured (including ensuring safety by dose reduction) after 3-day administration at the dose decided according to the specification for increasing the dose of tolvaptan (see [Section 3.2.2](#)), administration at that dose may be continued for up to 4 days (for up to 7 days in total).

In the case of an extended treatment with tolvaptan at reduced dose, the total number of administration days should be up to 7 days, which consists of “the days of administration at the dose just before the dose requiring reduction,” “the days of administration at the dose requiring reduction” and “the days of administration at the dose reduced to the next lower dose.”

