## **5.7 Definition of Evaluation Dose**

Of the doses administered as specified in [Section 3.2.2](#) and [Section 3.2.3](#), the dose meeting the following criteria is defined as an evaluation dose.

- 1) If sufficient increase in urine volume was obtained during the course of dose escalation, or if the dose was increased to 0.5 mg/kg/day because sufficient increase in urine volume was not obtained:
  - If the dose was not subsequently reduced, then that dose
  - If the dose was reduced without having been administered for 3 days, then the reduced dose
  - If the dose was reduced after having been administered for 3 days, then the dose before reduction

- 2) If IMP administration was discontinued before sufficient increase in urine volume was obtained during the course of dose increase:
  - The dose at final IMP administration

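### Every by-dose adverse event table uses the subject's evaluation dose; none shows events by the dose being taken at onset

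*SAP*

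**What the plan says.** SAP 9.2 plans two by-dose AE summaries: "The above AEs will also be summarized by evaluation dose. In addition, summaries of AEs by the evaluation dose after the start of administration" at that dose. Protocol 7.7.1 specifies the same two. In SAP Appendix 1 they become CT-8.3 and CT-9.3 (all treatment-emergent AEs) and CT-8.4 and CT-9.4 (events after the evaluation dose starts). Every one of these titles is by evaluation dose; the remaining AE tables are overall or by age group.

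SAP 5.7 gives each subject one evaluation dose. Rule 1 applies once the urine response is sufficient, "or if the dose was increased to 0.5 mg/kg/day because sufficient increase in urine volume was not obtained". The evaluation dose is then that dose, unless it is reduced:

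- Early reduction: "If the dose was reduced without having been administered for 3 days, then the reduced dose".
- Late reduction: "If the dose was reduced after having been administered for 3 days, then the dose before reduction".

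Rule 2 covers subjects who stop during escalation; their evaluation dose is the last dose given.

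Under SAP 3.2.2 every subject starts at 0.05 mg/kg/day and spends 2 days at each step that proves insufficient. At the top step the dose "will be increased to 0.5 mg/kg/day on Day 7, and administration at 0.5 mg/kg/day will be continued for 3 days". For extended treatment at a reduced dose, SAP 3.2.4 says "the total number of administration days should be up to 7 days", counting the step before the dose that needed reducing, that dose, and the reduced dose.

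SAP 9.1 reports exposure overall and by evaluation dose only. SAP 10, in contrast, tabulates drug concentrations by the dose on the sampling date.

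**The concern.** Safety and the choice of dose and regimen are both in the primary objective (SAP 2), so readers will use the by-dose AE tables to judge tolerability at each dose. A subject may take up to four doses but appears under one.

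The early-reduction rule matters most for interpretation. SAP 3.2.3 permits reductions for persistent thirst, dehydration, hypernatremia or other safety concerns. The event that prompts an early reduction begins at the higher dose, yet CT-8.3 and CT-9.3 show it under the lower one.

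Everyone takes 0.05 mg/kg/day, but the 0.05 column holds only subjects whose evaluation dose is 0.05. No table gives AE incidence on 0.05 for all who took it. Protocol 2.2 itself argues from thirst incidence by dose taken in the adult dose-ranging trial (21.4%, 27.3% and 53.6% at 15, 30 and 45 mg/day); the planned tables cannot be read that way wherever dose taken and evaluation dose differ.

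**Working it through.** The plan states no figure to reproduce here. The check counts days on which the dose taken differs from the evaluation dose, using SAP 3.2.2, 3.2.4 and 5.7.

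**Case 1: escalation, no reduction.** Days below the evaluation dose = 2 × (number of lower steps). Share = lower days / (lower days + n), where n is the number of days at the evaluation dose (3, or 7 with the full extension).

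| Evaluation dose (mg/kg/day) | Lower days | n = 3 | n = 7 |
|---|---|---|---|
| 0.05 | 0 | 0/3 = 0% | 0/7 = 0% |
| 0.15 | 2 | 2/5 = 40% | 2/9 = 22% |
| 0.3 | 4 | 4/7 = 57% | 4/11 = 36% |
| 0.5 | 6 | 6/9 = 67% | 6/13 = 46% |

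The 13 days agree with the longest treatment period in SAP 3.2.5. CT-8.3 and CT-9.3 count events on the lower days under the higher evaluation dose. CT-8.4 and CT-9.4 leave them out.

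**Case 2: reduction within 3 days of a dose that meets rule 1.** There are k = 1 or 2 days at the higher dose, then 3 at the reduced dose. The 7-day cap allows this: 2 + k + 3 = 6 or 7. For 0.5 reduced to 0.3, the course is 6 + k + 3 = 10 or 11 days, of which 1/10 = 10% or 2/11 = 18% lie above the evaluation dose. CT-8.3 and CT-9.3 count those days' events at 0.3.

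In CT-8.4 and CT-9.4 the outcome depends on when the evaluation dose starts, which the SAP does not define for this case. If it means the first day at the reduced dose, the events are left out. If it means first exposure to that level during escalation, they are counted at the lower dose. The first reading is the more natural: Protocol 3.2.4 says "The reduced dose should be regarded as the dose decided for each individual subject", and Protocol 3.7.1.5.1 has its own schedule headed "First Day of Administration at Reduced Dose".

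**Case 3: reduction after at least 3 days.** The cap gives 7 = 2 (previous step) + k (higher dose) + r (reduced dose).

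- k = 3: r = 2, so 2/5 = 40% of on-treatment days counted in CT-8.4 are at the lower dose.
- k = 4: r = 1, so 1/5 = 20%.
- k = 5: r = 0.

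Both sets of tables count these days' events at the higher dose.

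**Illustration of course length.** Assume the same daily AE risk p at every dose, 3 days at the evaluation dose and no reductions. Incidence = 1 − (1 − p)^days. CT-8.3 covers 3, 5, 7 and 9 treatment days across the four doses.

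- p = 0.05, treatment days only: 14.3%, 22.6%, 30.2% and 37.0%; ratio of highest to lowest 2.6.
- p = 0.05 plus 5 follow-up days: 33.7% to 51.2%, ratio 1.5. Plus 7 follow-up days: 40.1% to 56.0%, ratio 1.4. Protocol 5.7 collects AEs until 5 to 7 days after the last dose.
- Treatment days only, other risks: p = 0.02 gives 5.9% to 16.6%; p = 0.10 gives 27.1% to 61.3%.
- CT-8.4 at p = 0.05 is 14.3% in every column (treatment days only).

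The daily risks are assumptions; the documents give no pediatric AE rates.

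**The case against.** The evaluation-dose tables follow the protocol and are a coherent summary of a course titrated to a dose. Several features already narrow the gap:

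- For subjects with no reduction, CT-8.4 and CT-9.4 show on-treatment events at the dose taken. Reading them beside CT-8.3 exposes the course-length effect.
- For anyone who stops without a prior reduction, the evaluation dose is the dose at stopping. The discontinuation tables therefore mostly place such events correctly, except those that began at an earlier step.
- With no reduction and no missed days, subject-days at each dose can be worked out from the exposure table and the fixed 2-day steps. PDT-2.3.3 gives sodium and potassium by day and evaluation dose, which maps to dose taken in the same way.
- The 2.6 ratio ignores follow-up; 1.4 to 1.5 fits the AE collection window better.
- Dose at onset has its own faults: carry-over after a step, confounding with time on treatment and urine response, and 60 subjects spread over four doses.

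All of this stands and limits the effect. None of it yields AE incidence by dose at onset for escalation days or for subjects whose dose was reduced. Listings AE-1 and CT-9.7 to CT-9.9 do not fill the gap: the SAP gives only their titles, and listings carry no denominators.

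**Conclusion.** The concern holds. No planned table gives AEs by dose at onset with a matching denominator, and the three mismatches follow directly from the plan's own dosing and evaluation-dose rules. Cases 1 and 3 move events to a higher dose; case 2 moves them one step down.

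The day counts assume the scheduled steps with no missed doses. The net direction and size of any distortion are unknown, because AE rates and the number of reductions are not given. Primary efficacy is unaffected, and all treatment-emergent AEs remain in the overall and age-group tables. The change should be made as a supplement to the planned tables; it does not correct an error in them.

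**What to change.** Keep the evaluation-dose tables and make three changes to the SAP.

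1. **SAP 9.2.** Add treatment-emergent AE tables (all, related, serious, leading to discontinuation) by the dose of the last administration before onset. For each dose, show the number of subjects who took it as the denominator, and the subject-days at it. Count a subject once per preferred term per dose, at highest severity. Assign an event with no onset time on a dose-change day to that day's dose. Put events starting later than the day after final administration in a separate post-treatment column.
2. **SAP 9.1.** Add subject-days at each dose taken.
3. **SAP 5.7.** State that, after a reduction that makes the reduced dose the evaluation dose, the evaluation dose starts on the first day at the reduced dose.

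The cost is SAP wording and programming. Dose and administration time (SAP 3.2.1) and AE onset date (Protocol 5.2) are already recorded. Onset time is recorded only where possible, so the tie-break will be used. The carry-over and confounding noted above should be stated with the new tables.
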